4.1.2.1 Size/Accrual Rate

The planned accrual size is 157 evaluable patients across the three cohorts of patients. The expected accrual rate is 4 patients per month. However, given the possibility of early stopping, the sample size could be as low as 66 if all three cohorts stop in the first stage.

4.1.2.2 Analysis of Primary Endpoints

The frequency of best objective response (CR+PR) by 16 weeks will be calculated along with an exact 95% confidence interval.

4.1.2.3 Analysis of Secondary and Exploratory Endpoints

The frequency of radiographic response will be documented with summary statistics at the estimated MTD and by dose level. Best overall response rate (CR+PR) will be calculated along with a 95% confidence interval.

Progression-free survival (PFS) and overall survival (OS) curves will be generated using Kaplan-Meier methodology. PFS is defined as the time from enrollment until disease progression or death from any cause. Patients who are alive and have not progressed will be censored at the date of their last follow-up. OS is defined as the time from enrollment until death from any cause. Patients who are alive will be censored at their last follow-up.

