7.4 Duration of Follow Up

Participants will be followed for up to 5 years after completion or removal from study treatment or until death, whichever occurs first. Participants removed from study treatment for unacceptable adverse events will be followed until resolution or stabilization of the adverse event. A post-study follow-up contact via phone by site staff will be conducted every 3 months during years 1 and 2, then every 6 months thereafter to obtain information on any new anti-cancer therapy received and survival status.

A participant will be considered lost to follow-up if he or she fails to return for 3 scheduled visits and is unable to be contacted by the study site staff.

The following actions must be taken if a participant fails to return to the clinic for a required study visit:

- The site will attempt to contact the participant and reschedule the missed visit within 2 weeks, counsel the participant on the importance of maintaining the assigned visit schedule, and ascertain if the participant wishes to and/or should continue in the study.
- Before a participant is deemed lost to follow-up, the Investigator or designee will make every effort to regain contact with the participant (where possible, at least 3 telephone attempts). These contact attempts should be documented in the participant's medical record or study file.
- Should the participant continue to be unreachable, he or she will be considered to have withdrawn from the study with a primary reason of lost to follow-up.

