| Weight | X | X | X | X | X | X | X | X | X | X | X | X | X | |
| ECOG perf. status | X | X | X | X | X | X | X | X | X | X | X | X | X | |
| ECG ⁶ | X | | | X | | X | | X | | X | | | X | |
| LE Doppler Ultrasound | X | | | | | | | | | | | | | |
| ECHO or MUGA ⁷ | X | | | | | | X | | | | | | X | |
| CBC with differential ⁸ | X | X | X | X | X | X | X | X | X | X | X | X | | |
| Comprehensive metab. panel ⁸ | X | X | X | X | X | X | X | X | X | X | X | X | X | |
| Ophthalmologic exam ⁹ | X | | | | | | | | X | | X | | X | |
| PT/PTT | X | | | X | | | | | | | | | | |
| Fresh tumor biopsy ¹⁰ | X | | | X | | | | | | | | | X | |
| TSH, free T4, cortisol ¹¹ | X | | | | | X | | X | | X | | | X | |
| Viral Serology ¹² | X | | | | | | | | | | | | | |
| C-reactive protein | X | | | | | | | | | | | | | |
| LDH | X | | | | | | | | | | | | | |

Columbia University Irving Medical Center
Herbert Irving Comprehensive Cancer Center
AAAS4165_Version Date: 07/07/2021

| | | | | | | | | | | | | |
|---|---|---|---|---|---|---|---|---|---|---|---|---|
| CPK | X | | | | X | | X | | X | | X | |
| Ca 19-9 and/or CEA | X | | | | X | | X | | X | | X | |
| Pregnancy test ¹³ | X | | | | | | | | | | | |
| Urinalysis | X | | | | | | | | | | | |
| PBMC samples ¹⁴ | X | | | X | | | X | | | | X | |
| Tumor response assessment ¹⁵ | X | | | | | | X | | | | X | |
| Concomitant medications | X | X | X | X | X | X | X | X | X | X | X | |
| Adverse Events | | X | X | X | X | X | X | X | X | X | X | X |
| Atezolizumab administration ¹⁶ | | X | | X | | X | X | X | X | X | X | |
| Dispense cobimetinib | | X | | | | X | | X | | X | | |
| Dispense hydroxychloroquine | | X | | | | X | | X | | X | | |
| Dispense Enoxaparin | | X | | | | X | | X | | X | | |
| Review of dosing diary | | | X | X | X | X | | X | | X | | X |
| Survival follow-up | | | | | | | | | | | | X |
| Blood sampling for PK/PD ¹⁷ | | X | X | X | | X | | | | | | |

1. Protocol-specified screening procedures that are performed as part of standard of care and within 21 days of Day 1 of Cycle 1 may be used for screening purposes. Clinical laboratory studies and baseline CT scan must be performed within the 14-day period before Day 1 of Cycle 1. Screening labs may be used for Cycle 1 Day 1 if performed within 72 hours prior to study visit.
2. The End-of-Study (EOS) visit should be scheduled within the 28-day period after the last dose of study drug and before starting any new anti-neoplastic therapy.

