3. A post-study follow-up contact by phone by site staff will be conducted every 3 months during years 1 and 2, then every 6 months thereafter to obtain information on any new anti-cancer therapy received and survival status.
4. Initial diagnosis of adenocarcinoma and KRAS mutation status needs to be confirmed by a CLIA certified pathology.
5. A complete physical examination will be performed at screening. All subsequent physical examinations will be disease-specific on Cycle 1 days 1, 8, 15, 22; Cycle 2 and 3 days 1 and 15; day 1 and 15 on each subsequent cycle, and at the End-of-Study visit.
6. ECG will be performed after the patient has been in a supine position for at least 5 minutes. It will be performed at screening, cycle 1 day 15, day 1 of every subsequent cycle, and at the End-of-Study visit.
7. ECHO or MUGA scan should be performed at screening, day 1 of cycle 2, every 3 months (+ 1 week) thereafter and at the end of study visit.

Columbia University Irving Medical Center
Herbert Irving Comprehensive Cancer Center
AAAS4165_Version Date: 07/07/2021

8. A complete blood count with differential and comprehensive metabolic panel including glucose, calcium, albumin, total protein, sodium, potassium, CO2 (carbon dioxide, bicarbonate), chloride, BUN (blood urea nitrogen), creatinine, ALP (alkaline phosphatase), ALT (alanine amino transferase), AST (aspartate amino transferase) and bilirubin will be performed on Cycle 1 days 1, 8, 15, and 22; Cycle 2 and 3 days 1 and 15; on day 1 and 15 of each subsequent cycle, and at the End-of-Study visit.
9. An Ophthalmologic examination should be performed during the screening period, and on cycle 3 day 1 (+ 7 days), every 12 weeks (+ 7 days) thereafter, and at the End-of-Study visit if not performed within 6 weeks. The baseline exam should include: best corrected distance visual acuity (BCVA), an automated threshold visual field (VF) of the central 10 degrees (with retesting if an abnormality is noted), and spectral domain ocular coherence tomography (SD-OCT). Each subsequent examinations should include BCVA, VF and SD-OCT. In patients of Asian descent, it is recommended that visual field testing be performed in the central 24 degrees instead of the central 10 degrees.

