10. Fresh core tumor biopsy will be performed: (1) within 14 days of starting therapy but at least three days prior to starting therapy; (2) Cycle 1 week 3 (day 15-21); and (3) If the patient allows, at progression (within 4 days of discontinuation of therapy).
11. TSH, free T4, and AM cortisol will be assessed at screening, Day 1 of each cycle starting at C2, at end of study, and as clinically appropriate.
12. At screening, patients without a prior positive HIV test result will undergo an HIV test, unless not permitted per local regulations. Patients will also be tested for HBsAg, HBsAb, total HBcAb, and HCV antibody. If a patient has a negative HBsAg test and a positive total HBcAb test at screening, an HBV DNA test should be performed. If a patient has a positive HCV antibody test at screening, an HCV RNA test must also be performed to determine if the patient has an active HCV infection.
13. For women of child-bearing potential, a screening serum pregnancy test must be negative within 7 days of Day 1 of Cycle 1.
14. Peripheral blood mononuclear cells will be collected during screening, cycle 1 day 15, cycle 3 day 1, every eight weeks (+ 7 days), and at End-of-Service visit.
15. CT scan with contrast of the chest, abdomen, pelvis or CT chest and MRI of abdomen/pelvis, PET/CT, or appropriate imaging of disease site to assess tumor status will be performed. Imaging should be performed at the designated time for tumor assessment +/- 7 days. End of study needs not be performed if patient has radiological evidence confirming progression, but needs to be performed if patient coming off study for other reasons, except due to fatality.
Phase 1 –Imaging to be performed every 8 weeks (+ 7 days)
Phase 2 –Pancreas adenocarcinoma –Imaging to be performed every 8 weeks (+ 7 days)
Colorectal adenocarcinoma – Imaging to be performed every 12 weeks (+ 7 days)
Histology agnostic adenocarcinoma – Imaging to be performed every 8 weeks (+ 7 days)
16. The initial dose of atezolizumab will be delivered over 60 (+/- 15) minutes. Subsequent infusions will be delivered over 30 (+/-10) minutes if the previous infusion was tolerated without infusion-associated adverse events, or 60 (+/- 15) minutes if the patient experienced an infusion-associated adverse event with the previous infusion.
17. For pharmacokinetic (PK) analysis, whole blood for hydroxychloroquine and plasma for cobimetinib will be obtained on –
Cycle 1 Day 1 - Pre-morning dose, 1, 2, and 4 hours post-morning dose.

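### PFS is censored at last follow-up, but after the end-of-study scan scheduled follow-up is by phone without tumour assessment, so patients who leave treatment without progression add unverified progression-free time.

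*Combined protocol and SAP*

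**What the plan says.** Section 4.1.2.3 defines the endpoint and its censoring: "PFS is defined as the time from enrollment until disease progression or death from any cause", and "Patients who are alive and have not progressed will be censored at the date of their last follow-up". The next sentences censor OS at last follow-up too, so the natural reading is date of last contact for both. Section 12.11 defines PFS again without a censoring rule. Section 4.1.1.4 plans phase 1 PFS curves, also without one.

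Section 7.4 sets the follow-up: "Participants will be followed for up to 5 years after completion or removal from study treatment or until death, whichever occurs first". Its form is stated there ("A post-study follow-up contact via phone by site staff will be conducted every 3 months during years 1 and 2", then every 6 months) and repeated in footnote 3 of Table 10. The call's purpose is "to obtain information on any new anti-cancer therapy received and survival status".

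Imaging runs every 8 weeks, or every 12 for the colorectal cohort (Table 10, footnote 15). The same footnote waives the end-of-study scan once progression is confirmed radiologically, "but needs to be performed if patient coming off study for other reasons, except due to fatality". Footnote 2 gives the timing: "The End-of-Study (EOS) visit should be scheduled within the 28-day period after the last dose of study drug". Table 10 marks survival in the Follow-up column but no tumour response assessment.

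Sections 12.6 and 12.9 ask sites to try to document progression after discontinuation, but only for patients with global deterioration, and they set no scan dates.

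**The concern.** A PFS censoring date should be one on which the patient was known to be free of progression. A phone call about survival and new therapy cannot establish that. Under the rule as written, a patient who stops for toxicity, intercurrent illness or withdrawal after a clean end-of-study scan remains at risk for PFS although progression is no longer looked for. That can continue through subsequent anti-cancer therapy, because no rule addresses it.

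Progressions missed in this way stay in the denominator as progression-free time, so the bias is upward and grows with the share of patients who leave. PFS and safety are both phase 2 secondary objectives. A poorly tolerated regimen would show a flattered PFS curve for that reason alone.

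**Working it through.** The plan gives no PFS target, event count or power, so there is no figure to reproduce. The size below is an illustration.

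**1. Inputs**

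- Pancreas: median PFS 3.1 and OS 6.1 months (background, second-line pancreas regimen); scans every 8 weeks.
- Colorectal: median PFS 1.9 and OS 8.8 months (background, regorafenib); scans every 12 weeks (Table 10).
- Share leaving without progression, d: not given, so assumed at 21%, shown over 10% to 40%. Section 3.1.4.2 reports that 21% stopped treatment on atezolizumab plus cobimetinib. This is only a guide.
- Calls every 3 months. Accrual of 67 / 4, about 17 months, and at least 6 months' follow-up (assumed).
- Exponential times, leaving independent of progression, a clean scan on leaving, and no progression documented afterwards (all assumed).

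**2. Monthly hazards**

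Progression: λ = ln 2 / median PFS. Death after progression, k, solves (k·e^(−λt) − λ·e^(−kt)) / (k − λ) = 0.5 at the OS median. Leaving: μ = λd / (1 − d).

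- Pancreas, d = 21%: λ = 0.2236, k = 0.3480, μ = 0.2236 × 0.21 / 0.79 = 0.0594.
- Colorectal, d = 21%: λ = 0.3648, k = 0.1195, μ = 0.3648 × 0.21 / 0.79 = 0.0970.

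**3. Excess at 6 months by hand**

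The curve is inflated by patients who left before progressing, would have been seen to progress by the last scan before month 6 (τ = 5.52 months on either schedule), and are still alive at 6 months. With a = λ − k and b = λ + μ − k:

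excess = λ·e^(−6k) × [(1 − e^(−aτ)) / a − (1 − e^(−bτ)) / b]

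- Pancreas: 0.2236 × 0.1239 × (7.934 − 6.640) = 0.036.
- Colorectal: 0.3648 × 0.4882 × (3.024 − 2.480) = 0.097.

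**4. Simulation (400,000 patients per setting), 6-month Kaplan-Meier PFS**

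| Cohort | Leaving | Scans continued | As written | Censored at last assessment* |
|---|---|---|---|---|
| Pancreas | 10% | 0.289 | 0.304 | 0.278–0.283 |
| Pancreas | 21% | 0.290 | 0.324 | 0.264–0.276 |
| Pancreas | 30% | 0.289 | 0.340 | 0.246–0.265 |
| Pancreas | 40% | 0.287 | 0.360 | 0.221–0.250 |
| Colorectal | 10% | 0.132 | 0.174 | 0.122–0.125 |
| Colorectal | 21% | 0.134 | 0.227 | 0.110–0.116 |
| Colorectal | 30% | 0.133 | 0.271 | 0.096–0.106 |
| Colorectal | 40% | 0.133 | 0.328 | 0.079–0.095 |

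*The range covers two conventions: later deaths ignored, or counted only within two scan intervals of the last scan.

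At 21% the excess is 3.4 points (pancreas) and 9.3 (colorectal), close to the hand figures. The small difference arises because some leavers are censored at a call before month 6. A leaver carries on average 5.5 (pancreas) or 7.2 (colorectal) months of PFS time after the last scan, of which about 1.95 and 4.7 fall after the unseen progression.

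**5. Median**

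Pancreas stays at 3.7 months and reaches 4.0 only at 40% leaving. Colorectal stays at 2.8 throughout. This is because median PFS is tied to scan dates. Section 4.1.2 gives 8-week scans for all cohorts. On that schedule the colorectal curve lies near e^(−0.3648 × 1.84) = 0.51 after the first scan, and its median would be unstable under any rule.

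**6. Deaths after the last scan**

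A rerun of the same model at 21% moved only living patients back to their last scan and counted every death whenever it occurred. It gave about 0.30 (pancreas) and 0.18 (colorectal). That removes only part of the inflation, so the handling of late deaths needs an explicit rule.

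**The case against.** The strongest reply is that the protocol does look at disease status on exit. Footnote 15 requires an end-of-study scan for patients leaving for reasons other than progression, so unverified time starts only after it. Sections 12.6 and 12.9 add an effort to document progression after symptomatic deterioration. Section 13.5 has monitors verify progression dates and subsequent treatments. A progression found in routine care would count as an event. All of this is correct and narrows the gap, but none of it schedules a tumour assessment after the end-of-study scan.

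A reader might therefore infer that progression can never be recorded off treatment, or that every such patient's PFS becomes OS. The documents do not support that: progression may be documented outside the schedule. The illustration assumes it never is, so for a given leaving rate it leans towards the larger bias.

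It is also fair to say that PFS is a secondary, single-arm, descriptive curve with no threshold, that the protocol names no 6-month landmark, and that last-assessment censoring has its own error. In the model that error is downward: 1.4 to 2.6 points at 21% for pancreas and 1.8 to 2.4 for colorectal. The gain is clear for colorectal and modest for pancreas. At 40% leaving in pancreas the downward error (3.7 to 6.6 points) approaches the upward error of the present rule (7.3).

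**Conclusion.** The point holds for the PFS curve. As written, the censoring rule carries patients who leave without progression past their last disease assessment, and it inflates landmark rates and the tail. With 21% leaving, the 6-month rate is overstated by about 3 points for pancreas and 9 for colorectal. Over 10% to 40% leaving, the as-written readings are 30% to 36% against 29%, and 17% to 33% against 13%. These sizes rest on an assumed leaving rate, background medians from other regimens, and leaving that is independent of progression; the direction does not depend on the particular rate.

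Two wider readings should be resisted. The plan does not put the primary endpoint at risk: response by 16 weeks and the Simon stopping rules do not use PFS. Nor does this show an inflated median, which hardly moves on the Table 10 schedule. The change is worth making before phase 2 opens, but nothing in the phase 2 decision depends on it.

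**What to change.** In Section 4.1.2.3, state that patients without documented progression or death are censored for PFS at their last evaluable tumour assessment, including the end-of-study scan. Apply the same rule to the phase 1 curves in Section 4.1.1.4. Keep last-contact censoring for OS only.

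Prespecify two further items, each with a sensitivity analysis, since statisticians differ on the convention: how new anti-cancer therapy is handled, and how a death after missed or discontinued assessments is counted. The present definition counts death from any cause without a time limit, so any limit should be a deliberate choice. Scheduled scans until progression for patients who stop for other reasons would address the cause directly, at the cost of extra imaging.

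In the same edit, reconcile the PFS start date (enrollment in 4.1.2.3, start of treatment in 12.11) and the colorectal scan interval (8 weeks in 4.1.2, 12 in Table 10).

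The cost is a few sentences, and Sections 1 and 4.1.2 already require an amendment before phase 2 activation. PFS will look less favourable and may read about 1 to 3 points low at 21% leaving, more if more patients leave. Reporting the number who leave without progression, by cohort, would let readers judge this.

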4.2 Number of Patients

Phase 1: N=18

Phase 2: N=157 (66-157)

5. SUBJECT SELECTION AND WITHDRAWL

Each of the criteria in the following section must be met in order for a patient to be considered eligible for participation.

5.1 Inclusion Criteria

For *Phase 1 and 2*, participants must have histologically confirmed KRAS-mutant malignancy that is metastatic or unresectable, and for which standard curative or meaningful life prolonging palliative measures do not exist or are no longer effective as described below (#3). Subjects with pancreas adenocarcinoma or colorectal adenocarcinoma have specific requirements. **At least 12 of the 18 evaluable patients within phase 1 should carry an active diagnosis of either pancreas or colorectal adenocarcinoma.**

Specific inclusion criteria are:

1. Histological or pathological confirmation of malignancy with a KRAS-activating mutation.

Cytologic or histologic proof of malignancy needs to be verified by the treating institution pathologist, either from the initial diagnostic biopsy or from the required pre-treatment biopsy, prior to initiation of any study-related therapy. Tumor must contain an activating KRAS mutation as determined by an FDA or New York State approved non-significant risk assay (within exons 2, 3, and 4). Subjects may be enrolled using prior *KRAS* positive result by non-FDA or New York State approved assay obtained per standard of care, but may not initiate treatment until *KRAS* mutation is confirmed by an FDA or New York State approved assay. FDA approved mutational analysis tests performed on blood which identify a KRAS mutation along with a biopsy which confirms tumor histology will be sufficient to meet this criteria. Please note, there is specific interest in KRAS G12R mutated patients with pancreas cancer or colorectal cancer.

2. Extent of disease

Advanced disease for which no curable options are available, including but not limited to, surgery, radiation, or loco-regional therapy. Subjects who are not deemed candidates for these curative therapies will be eligible if they meet other criteria.

3. Prior treatments

• Pancreas adenocarcinoma

Subjects must have progressed on or be intolerant of combination therapy containing either 5-Fluorouracil/Capecitabine- and/or gemcitabine-based therapy. Subjects who experienced disease recurrence while receiving adjuvant chemotherapy or within three months of completing adjuvant chemotherapy are eligible.

• Colorectal adenocarcinoma

Subjects must have progressed on or be intolerant of combination therapy containing 5-Fluorouracil/Capecitabine, and must have received Oxaliplatin and Irinotecan.

• MSI-H/dMMR or NTRK-fusion positive tumors

Subjects must have received prior treatment with approved drugs for tumors harboring these aberrations.

• Histology agnostic cancers other than pancreas and colorectal adenocarcinoma (see above; Phase 1 and 2)

Subjects must have progressed on or be intolerant of all standard of care therapies that result in a median progression free survival benefit of ≥ 8 weeks, or overall response rate of $>5\%$.

Columbia University Irving Medical Center
Herbert Irving Comprehensive Cancer Center
AAAS4165_Version Date: 07/07/2021

4. ECOG performance status of 0 or 1
5. Age \geq 18 years
6. Adequate hematological and end-organ function (test results from within 14 days prior to initiation of study treatment):
 - ANC $\geq 1.5 \times 10^9/L$ without granulocyte colony-stimulating factor support
 - WBC count $\geq 2.5 \times 10^9/L$ (2500/ μL)
 - Lymphocyte count $\geq 0.5 \times 10^9/L$ (500/ μL)
 - Platelet count $\geq 100 \times 10^9/L$ (100,000/ μL) without transfusion
 - Hgb $> 9.0 \text{ g/dL}$
 - AST, ALT, and alkaline phosphatase (ALP) $\leq 2.5X$ upper limit of normal (ULN), unless elevated secondary to biliary obstruction from the pancreas mass and amenable to decompression prior to initiation of therapy
 - Serum total bilirubin $\leq 1.5X$ ULN, unless in patients with known Gilbert disease ($\leq 3X$ ULN), or unless elevated secondary to biliary obstruction from the pancreas mass and amenable to decompression prior to administration of investigational therapy
 - Albumin $\geq 3.0\text{g/dL}$
 - Creatinine within ULN or calculated creatinine clearance (CrCl) $>50 \text{ mL/min}$ using the Cockcroft-Gault formula
 - INR and aPTT $\leq 1.5X$ ULN except for those who are on stable anticoagulation for at least three months.
7. Measurable disease according to IM-RECIST and tumor accessible for fresh biopsy if ten adequate paired biopsied specimens have not been procured (Phase 1)
8. Negative pregnancy test

Women of childbearing potential must have a negative serum pregnancy test at screening and must agree to use an effective form of contraception from the time of the negative pregnancy test until a minimum of 3 months after the last dose of study drug. Effective forms of contraception include abstinence, hormonal contraceptive (injectable or implantable) in conjunction with a barrier method, or a double barrier method. Women of non-child-bearing potential must have been postmenopausal for ≥ 1 year or surgically sterile.

9. Birth control agreement

Fertile men must agree to use an effective method of birth control during the study and for up to 3 months after the last dose of study drug.

10. Informed consent

Participants must be willing and able to provide written informed consent prior to any study-related procedures and to comply with all study requirements.

11. Ability to comply

Columbia University Irving Medical Center
Herbert Irving Comprehensive Cancer Center
AAAS4165_Version Date: 07/07/2021

Participants must be able to comply with the study protocol, according to the investigator's judgement.

12. DVT testing

Participants must have undergone lower extremity dopplers to rule out deep venous thrombosis (DVT) within the screening period, and undergo therapeutic anticoagulation if evidence of DVT is identified.

13. VTE testing

Patients deemed at increased risk of venous thromboembolism (VTE) based on primary cancer, which includes pancreas adenocarcinoma, gastric/GE junction adenocarcinoma, or CNS malignancy, and have not been taking anticoagulants, are to undergo prophylaxis anticoagulation with enoxaparin. Enoxaparin will be administered at a dose of 1mg/kg/day to mitigate the risk of VTE. Subjects who are unable to receive enoxaparin, but deemed at increased risk of VTE will not be eligible and consultation with the Principal Investigator is required.

14. Anticoagulation treatment

Subjects who are currently stable on full-dose anticoagulation medication for at least 8 weeks are considered eligible. However, subjects who have an increased clot burden on full-dose anticoagulation, such as central pulmonary embolism, or peripheral pulmonary embolism, and DVT within the extremities will be considered eligible only with the approval of the Principal Investigator.

